### **Concomitant Medications:**

Concomitant medications are allowed if not listed in [Table-1](#). Oral corticosteroids will be allowed as a rescue medication. Stable doses of oral corticosteroids will be permitted at enrollment of the study, with a maximum dose not to exceed 20mg/day of prednisone or its equivalent. For patients on oral corticosteroids, Calcium 1200mg and Vitamin D 800 IU will be prescribed. For individuals with recurrent cellulitis or recurrent candidiasis, antimicrobials will be prescribed (see Exclusion Criteria). Dose adjustments of these medications should be avoided during the study. Drug-induced cases of BP will be excluded. Subjects who are receiving treatments known to worsen BP (angiotensin converting enzyme inhibitors & furosemide) must be on stable dose for at least 4 weeks prior to enrollment. Topical corticosteroids (TCS) are not allowed during the entirety of the study. Oral corticosteroids, as a rescue means (see [Supplemental 4](#)), will be allowed. After the screening period, the use of concomitant medication for BP in all body regions is restricted to bland emollients and other non-medicated interventions (not listed in [Table-1](#)) Use of bland emollients must be recorded. Preferred

emollients include Vaseline, Vanicream, and Vaniply. The definition of “bland” excludes all topical medications that contain pharmacologically active ingredients. Once the subject is screened and if the subject has intolerable blistering, scaling, and/or itching, the use of bland emollients is permitted. The use of bland emollients should be avoided during the 12 hours preceding a scheduled study visit.

**Inclusion/Exclusion Criteria:**

Subjects eligible for inclusion in this study have to fulfill **all** of the following criteria:

- Subjects must be able to understand and comply with the requirements of the study and communicate with the investigator. Subjects must give written, signed, and dated informed consent before any study related activity is performed. When appropriate, a legal representative will sign the informed consent according to local laws and regulation
- Both men and women must be at least 18 years of age at the time of screening
- Subjects must have clinical, histological, and serological features of BP
  - Urticarial plaques and/or vesicles and bullae
  - Characteristic eosinophilic spongiosis and/or subepidermal separation of the skin
  - Positive direct immunofluorescence (IgG and/or C3 at the basement membrane zone) or indirect immunofluorescence (IgG on the roof of salt- split skin) or positive serologies on ELISA for BPAG1 or BPAG2
- Subjects must have treatment naïve BP or treatment refractory disease, as defined by failure of at least one established treatment for BP
- Candidate for systemic therapy, defined by
  - Involvement of greater than 5% body surface area or moderate to extensive disease as defined by: the mean number of new bullae and urticarial plaques that have appeared over the course of 3 days as determined by the investigator or referring physician (moderate disease defined by  $> 1$  and  $\leq 10$  new bullae and  $\geq 5$  urticarial plaques and extensive disease by  $>10$  new bullae)
  - Failure of prior therapy
    - Topical treatment
    - Systemic immunosuppressant
    - Oral antibiotics and/or niacinamide

Subjects fulfilling **any** of the following criteria are not eligible for inclusion in this study. In order to ensure the recruitment of a representative sample of all eligible subjects, the investigator may apply no additional exclusions.

- Forms of BP other than classic BP (e.g. mucous membrane BP, Brunsting-Perry BP, p200 BP, p105 BP, or BP with concomitant pemphigus vulgaris)
- Drug-induced BP (e.g., new onset or current exacerbation from angiotensin converting enzyme inhibitors, penicillamine, furosemide, phenacetin)
- Subjects who are receiving treatments known to worsen BP and use of penicillamine or phenacetin and those on angiotensin converting enzyme inhibitors or furosemide who have not been on a stable dose at least 4 weeks prior to enrollment.
- Ongoing use of prohibited treatments. Washout periods detailed in [Table-1](#).
- Previous exposure to Taltz (Ixekizumab) or any other biologic drug directly targeting IL-17A or IL-17RA
- Use of any other investigational drugs within 5 half-lives of the investigational treatment before study drug initiation or until the pharmacodynamics effect has returned to baseline, whichever is longer
- Previous use of IL-20 monoclonal antibody
- Pregnant or nursing (lactating) women (pregnancy is defined as the state of a female after conception and until the termination of gestation, confirmed by a positive human chorionic gonadotropin (hCG) laboratory test)
- Women of childbearing potential [Post-menopausal or not of child-bearing potential is defined by: 1 year of natural (spontaneous) amenorrhea or Surgical bilateral oophorectomy (with or without hysterectomy), total hysterectomy or tubal ligation at least 6 weeks ago. Oophorectomy alone must confirmed by follow up hormone level assessment to be considered not of child-bearing potential, defined as all women

physiologically capable of becoming pregnant, unless they are using basic methods of contraception which includes:

- Total abstinence (Periodic abstinence and withdrawal are not acceptable methods of contraception)
- Female sterilization (bilateral oophorectomy with or without hysterectomy), total hysterectomy, or tubal ligation at least 6 weeks before taking study treatment. Oophorectomy alone requires follow up hormone level assessment for fertility.
- Male sterilization (at least 6 months prior to screening). The vasectomized male partner should be the sole partner for that subject.
- Barrier methods of contraception: condom or occlusive cap.
- Use of oral, injected or implanted hormonal methods of contraception or other forms or hormonal contraception that have complete efficacy (failure <1%). (The dose of the contraceptive should be stable for 3 months)
- Active ongoing inflammatory diseases of the skin other than BP that might confound the evaluation of the benefit of Taltz (Ixekizumab)
- Underlying condition (including, but not limited to metabolic, hematologic, renal, hepatic, pulmonary, neurologic, endocrine, cardiac, infectious or gastrointestinal conditions) which, in the opinion of the investigator, significantly immunocompromises the subject and/or places the subject at unacceptable risk for receiving an immunomodulatory therapy
- Investigator discretion should be used for subjects with pre-existing or recent-onset central or peripheral nervous system demyelinating disorders
- Significant medical problems, including but not limited to the following: uncontrolled hypertension, congestive heart failure (New York Heart Association [NYHA] status of class III or IV)
- Serum creatinine level exceeding 2.0 mg/dL (176.8  $\mu\text{mol/L}$ ) **at screening**
- Total white blood cell (WBC) count <2,500/ $\mu\text{L}$ , platelets <100,000/ $\mu\text{L}$ , neutrophils <1500/ $\mu\text{L}$  or hemoglobin <8.5 g/dL, **at screening**
- Active systemic infections during the 2 weeks prior to randomization (common cold viruses not included) or any infection that reoccurs on a regular basis.
  - All patients should be specifically questioned in regards to a history of recurrent cellulitis or recurrent bacterial skin infections.
    - A history of recurrent cellulitis
      - Swab for MRSA carrier status
        - If positive, decolonization
          - Intranasal mupirocin 2% twice daily for 5 days
          - Chlorohexidine 2-4% wash daily for 5 days
        - Anti-streptolysin O (ASO) & Anti-DNA B (ADB) testing to be performed
          - If positive, place patient on prophylactic oral antibiotics for the duration of the study
            - Penicillin non-allergic
              - Penicillin VK 250mg BID (19)
            - Penicillin allergic
              - Clindamycin 150mg daily (20)
  - All patients should be screened for a history of oral, vaginal, or cutaneous candidiasis
    - A history of recurrent, clinically significant disease
      - Swab affected area for candida culture
        - If positive, prophylactic dosing of oral antifungals for the duration of the study
          - 150mg fluconazole weekly (21, 22)
  - Investigator discretion should be used regarding subjects who have traveled or resided in areas of endemic mycoses, such as histoplasmosis, coccidioidomycosis or blastomycosis and for subjects with underlying conditions that may predispose them to infection, such as advanced or inadequately controlled diabetes. Due to its endemic nature in Arizona, coccidioidomycosis screening is

performed at baseline. A history of a disseminated coccidioidomycosis infection will exclude subjects.

- Positive coccidioidomycosis Enzyme Immunoassay (EIA) IgG and/or IgM with positive complement fixation **at screening** and deemed by infectious disease to be inappropriate for therapy
  - Subjects with a positive coccidioidomycosis should undergo a full coccidioidomycosis work up and treatment should not be initiated until infectious disease specialists clear the subject.
- History of an ongoing, chronic or recurrent infectious disease, or evidence of tuberculosis infection as defined by a positive or indeterminate QuantiFERON TB-Gold test (QFT) **at screening**.
  - Subjects with a positive QFT test may participate in the study if a full tuberculosis work up (according to local practice/guidelines) is completed within 12 weeks prior to establishes conclusively that the subject has no evidence of active tuberculosis.
  - If the presence of latent tuberculosis is established, then treatment must have been initiated and maintained according to local country guidelines for at least 4 weeks prior to randomization.
- Past medical history of, or current infection with, human immunodeficiency virus (HIV), hepatitis B or hepatitis C prior to new diagnosis **at screening**
- History of lymphoproliferative disease and/or any known malignancy and/or history of malignancy of any organ system within the past 5 years
  - Exceptions include:
    - For skin squamous cell carcinoma in situ and/or well differentiate squamous cell carcinoma and/or basal cell carcinoma and/or actinic keratosis and/or melanoma in situ that have been treated with no evidence of recurrence
    - For the cervix carcinoma that has been removed
    - For the colon non-invasive malignant colon polyps that have been removed
- Current severe progressive or uncontrolled disease which the investigator renders the subject unsuitable for the trial or puts the subject at increased risk
- Inability or unwillingness to undergo repeated venipuncture
- Any medical or psychiatric condition which, in the investigator's opinion, would keep the subject from adhering to the protocol or completing the study per protocol
- History or evidence of ongoing alcohol or drug abuse, within the last 6 months prior to the initiation of therapy
- Plans for administration of live vaccines during the study period or in the 12 weeks prior to the initiation of therapy
- BCG vaccination within 12 months of starting the study or with 12 months after completing the study

### **Primary and Secondary Measures:**

All efficacy assessments will be performed prior to the administration of study treatment at each visit. The recommended order and the overall outline of measurements for the efficacy assessments are described below.

#### **Efficacy measures:**

- Cessation of new blisters.
- BPDAI (6)
- Total dose of prednisone required during phases of treatment
- anti-BP180 IgG and anti-BP230 IgG levels by ELISA
- Neutrophil and eosinophil counts
- IL-6, -17, -22, -23, TGFb, and MMP-9 levels in the serum and blister fluid

#### **Primary Outcome Measures:**

Median time from first dose of Taltz (Ixekizumab) treatment to cessation of new blisters. The study subject will undergo physical examination and assessment for cessation of new blister formation via physical examination and standard full body photography.

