#### **Statistical Analysis Plan:**

**Design:** This is an exploratory single center, open-label design study in approximately 12 patients. Safety of Taltz (Ixekizumab) in the treatment of the autoimmune blistering disease, BP will be evaluated. Changes in new blister formation will also be explored.

**Primary Endpoint:** The primary endpoint will be median time from first dose of Taltz (Ixekizumab) treatment to cessation of any new blisters.

**Secondary Endpoint(s):** The secondary endpoints will include change in BPDAI from day 0 to week 12, total dose of prednisone required during the therapeutic time period at weeks 0-12. Additional analysis will be performed on serological markers, disease activity after drug discontinuation, and safety monitoring. Descriptive statistics and graphical plots will be mainly used to summarize the data and estimate primary and secondary endpoints.

**Primary Analysis:** Calculation of the time from first dose of treatment until cessation of any new blisters will be conducted and summarized using means, standard deviations and 95% confidence intervals. Blister formation will be summarized at baseline and subsequent time points (using means, standard deviations and 95% confidence intervals). Change in blister formation (any new blisters) from baseline will be calculated by subtracting the baseline number of blisters from the number of blisters at each evaluation. Graphical displays will be produced; such as mean profile plots or bar charts.

**Secondary Analyses:** Analyses for secondary endpoints will also be descriptive in nature. Adjustment for multiple comparisons for the secondary analyses will not be done due to the exploratory nature of this research. Calculation of the change in BPDAI score from baseline to week 12 will be conducted and summarized using means, standard deviations and 95% confidence intervals. Graphical displays will be produced; such as mean profile plots or bar charts.

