## **Supplementals:**

### **Supplemental 1: Appropriateness of Measures**

According to expert consensus guidelines on BP, new blister formation is a defining feature of disease activity. (6) Disease control is defined as the cessation of new blister formation. The consolidation phase is defined as the phase with no new blister formation in 2 weeks and healing of lesions. Transient lesions heal within 1 week and non-transient lesions are does not heal within 1 week. Complete remission is defined by, no new blisters within 2 months, on or off therapy. Partial remission is defined by transient lesion formation. New, mild disease activity is defined by the formation of less than 3 lesions per month and a disease flare is defined by 3 or more lesions in a month. Therefore, we will be required to monitor for the time to cessation of new blisters as surrogate for disease control as well as the formation of new blisters throughout the study.

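### The primary event, cessation of new blisters, has no stated look-back and no rule for re-blistering before week 12, so a clear 2-weekly visit can be counted as cessation while blistering continues

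*Combined protocol and SAP*

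**What the plan says.** Primary Outcome Measures gives the endpoint as "Median time from first dose of Taltz (Ixekizumab) treatment to cessation of new blisters" and the ascertainment as "The study subject will undergo physical examination and assessment for cessation of new blister formation via physical examination and standard full body photography". The Statistical Analysis Plan repeats the endpoint with one added word: "The primary endpoint will be median time from first dose of Taltz (Ixekizumab) treatment to cessation of any new blisters".

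Table-2 schedules physical examination and photography at Day 0, at weeks 2, 4, 6, 8, 10 and 12, and at week 18. That gives six assessments after the first dose during treatment.

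Supplemental 1 supplies the clinical basis. It states "Disease control is defined as the cessation of new blister formation", with no duration attached, and links the endpoint to that state: "Therefore, we will be required to monitor for the time to cessation of new blisters as surrogate for disease control". It also states "Transient lesions heal within 1 week". Durations appear there only for other states, namely 2 weeks for consolidation and 2 months for complete remission.

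None of these sections gives a look-back period, a patient report of new blisters between visits, or a rule for blisters that return before week 12.

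**The concern.** A 2-weekly examination shows the skin on one day. A blister that formed a few days after the previous visit and healed within a week may leave nothing that an examiner or a photograph would identify as a new blister. A clear visit is therefore not the same as an interval without new blisters, and the plan does not say which of the two is the event. Two assessors could date the same patient differently and both be following the protocol.

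The same gap affects persistence. If a patient is clear at week 4 and blistering at week 6, nothing says whether the event stays at week 4, moves or is cancelled.

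This is the only primary endpoint, in an open-label, single-arm study. Research Design acknowledges assessment bias and relies on new blister formation as one of the objective measures that should limit it. Sample Size Computation says the estimates will be used to plan future studies. A time to cessation that runs early would carry into that planning, and there is no control arm to reveal it.

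**Working it through.** The plan has no figure to reproduce. The 12 patients are set on logistical and financial grounds, and no cessation rate is assumed. The calculation below illustrates what the stated method allows.

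**Inputs from the documents**
- Six post-dose visits, weeks 2 to 12 (Table-2).
- New bullae are counted over 3 days at entry, and moderate disease starts above 1 and runs to 10 (Inclusion/Exclusion Criteria). I use 1, 2 and 3 per 3 days.
- A flare is 3 or more lesions in a month (Supplemental 1). I take 3/30 = 0.1 per day as a low rate. It is relevant because patients can also qualify on body surface area, without a minimum number of bullae.

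**Assumptions not in the documents**
- New blisters follow a Poisson process at a constant rate λ per day, with no drug effect.
- An assessment detects every new blister of the last d days and none older. I vary d over 3, 7 and 14 days. These windows do not overlap at 2-weekly visits, so visits are independent.

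**Formulas**
- Chance that one visit is clear: p = exp(−λd).
- Chance of at least one clear visit in six: 1 − (1 − p)^6.

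**Worked case, 2 new bullae per 3 days**
- d = 3: p = exp(−2) = 0.135, and 1 − 0.865^6 = 0.58, or 7.0 of 12 patients.
- d = 7: p = exp(−4.67) = 0.0094, and 1 − 0.9906^6 = 0.055, or 0.7 of 12.
- d = 14: p = exp(−9.33) = 0.00009, giving 0.0005, or fewer than 0.1 of 12.

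**Chance of at least one clear visit by week 12, with no true cessation**

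| Rate of new blisters | 3-day look-back | 7-day | 14-day |
|---|---|---|---|
| 3 per 3 days | 26% | 0.5% | about 0 |
| 2 per 3 days | 58% | 5.5% | 0.05% |
| 1 per 3 days | 94% | 46% | 5.5% |
| 3 per 30 days | over 99% | 98% | 82% |

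**Persistence.** Clearance that lasts to week 12 requires the week 12 visit to be clear, so under the same assumptions its chance is p.
- At 3 per 30 days with a 14-day look-back, p = exp(−1.4) = 0.25, against 82% for any one clear visit.
- At 1 per 3 days with a 7-day look-back, p = exp(−2.33) = 0.10, against 46%.

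The table shows two things. Extending the look-back to the full visit interval removes most of the problem at 1 or more new bullae per 3 days. It does not remove it at low activity, where a clear fortnight can occur by chance and only a check on persistence helps.

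**The case against.** The strongest reply is that serial full body photographs already imply a look-back. New must be relative to something, and the previous photograph is the natural reference. On that reading, with complete capture, the chance is 0.05% at 2 per 3 days and 5.5% at 1 per 3 days. This is a fair reading, but the protocol never states it. Comparing two photographs taken 14 days apart would also miss a lesion that arose and healed between them. If this is the intent, writing it down is most of the fix.

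A second reply is that disease control, as Supplemental 1 defines it, carries no duration, and that later activity is a separate state there. This stands. Re-blistering need not cancel the event, and the plan is entitled to a first-cessation endpoint. The consolidation criterion ("The consolidation phase is defined as the phase with no new blister formation in 2 weeks and healing of lesions") is a different state that also requires healing, so it does not justify a 2-week rule here. The case for a between-visit look-back rests on the visit spacing alone.

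Third, recurrence would be partly visible. Supplemental 1 commits to monitoring new blisters throughout, and the Statistical Analysis Plan summarises blister formation at each time point. That is true at group level. It does not give the number of patients who blister again before week 12, and it does not say how their event times are treated. Secondary Outcome Measures lists first onset of new blisters only after the drug is stopped.

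Fourth, 2-weekly visits also record true cessation up to 2 weeks late, which pulls the other way. This stands, and it is a reason to report the event as an interval.

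Finally, the study is small and descriptive, with no decision threshold. That limits the consequences, but the event still needs a definition.

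**Conclusion.** The concern holds as a gap in ascertainment. The method, as written, permits a clear visit to be counted as cessation while blisters continue to form between visits, and it is silent on re-blistering before week 12.

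The size cannot be fixed from the documents. At 2 new bullae per 3 days the chance of at least one clear visit runs from 58% to 5.5% to 0.05% as the assumed look-back goes from 3 to 7 to 14 days. At 1 per 3 days it runs from 94% to 46% to 5.5%. These figures rest on a constant Poisson rate and no drug effect. The problem is material at low to moderate activity with a short look-back, and small at high activity with a long one.

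A reader might infer three stronger things that the documents do not support:
- That the protocol adopts a single-visit rule. It does not; it leaves the event undefined.
- That any lull between visits counts. A lull has to reach a visit to be seen.
- That 58% is the expected rate of false cessation. That figure needs a 3-day window. The 3 days in the entry criteria are a counting period for new bullae, not the time for which a blister can be recognised as new.

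**What to change.** 1. Define the event as the first scheduled visit at which no new blister has formed since the previous scheduled visit. Judge this by patient report (one CRF question), examination, and comparison with the previous visit's photographs. Day 0 photographs serve as the reference for week 2.
2. Record the event as lying between the last visit with new blisters and the first visit without, rather than as an exact day.
3. Report how many patients blister again by week 12 after meeting the event.
4. Add a sensitivity analysis that counts only cessation sustained to week 12. Item 1 alone does not address persistence, because a patient who re-blisters would keep the early time. State that a patient first clear at week 12 meets this condition with a single visit.

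The cost is one CRF question per visit and a few sentences in the SAP. Examination and photography are already scheduled, so no visits or procedures are added. The downside is that event times may be later and fewer patients may be counted as ceased. This is a cheap improvement.

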
#### **Sample Size Computation and Power Analysis:**

The sample size for this pilot study is set at 12 patients for logistical and financial reasons. This is similar in size to other exploratory studies and will provide adequate data for estimation purposes for planning future studies. With 12 patients, the study is intended to be for estimation purposes only.

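### Time to cessation of new blisters is interval-censored by the visit schedule, but it is to be summarised as an exact time with no rule for dating it

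*Combined protocol and SAP*

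**What the plan says.** The Statistical Analysis Plan states: "The primary endpoint will be median time from first dose of Taltz (Ixekizumab) treatment to cessation of any new blisters". Primary Outcome Measures says how it is ascertained: "assessment for cessation of new blister formation via physical examination and standard full body photography". Primary and Secondary Measures ties efficacy to visits: "All efficacy assessments will be performed prior to the administration of study treatment at each visit". Table-2 places examination and photography at Day 0, Weeks 2, 4, 6, 8, 10 and 12, and Week 18.

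Supplemental 1 links the event to disease control: "Disease control is defined as the cessation of new blister formation". It separately describes a consolidation phase that needs 2 weeks without new blisters, and does not connect that window to the primary endpoint.

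The Primary Analysis paragraph reads: "Calculation of the time from first dose of treatment until cessation of any new blisters will be conducted and summarized using means", followed by standard deviations and 95% confidence intervals. The documents do not say which visit or date counts as cessation, whether a blister-free period is required, or how the gap between visits is handled. They mention no diary and no recorded date of the last new blister.

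**The concern.** A patient found clear at Week 6 stopped blistering at some unknown time before that visit. If the visit date is entered as the event time, the error always runs in the same direction and does not shrink with more patients. A confidence interval built from visit dates reflects the spread of those dates but not the shift, so it looks more reliable than it is.

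This is separate from patients who never stop or who relapse. It arises even when all 12 patients stop for good during treatment.

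What is at stake is the estimate itself. The sample size section says "With 12 patients, the study is intended to be for estimation purposes only" and offers the results for planning later studies. A shift of 1 to 3 weeks is large against a 12-week treatment epoch, and its size would depend on an unwritten choice at the site.

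**Working it through.** **The plan's own figure.** There is none to reproduce: "The sample size for this pilot study is set at 12 patients for logistical and financial reasons". No precision target, SD or distribution of times is given.

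**Inputs.** n = 12; visits every 14 days to Week 12, then Week 18 (Table-2). Assumptions: blistering truly and permanently stops, T is the day of the last new blister, and the unspecified 95% interval is a t interval.

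**Delay under two visit-dating rules, to Week 12.**
- First clear visit (no fresh blister that day): D = 14 × ceil(T/14). The delay D − T is 0 to 14 days, on average 7 if T is spread evenly within the gap.
- Visit closing a wholly clear interval (none since the previous visit): D = 14 × ceil(T/14) + 14. The delay is 14 to 28 days, on average 21 = 14 (blister-free window) + 7 (visit grid).
- Example: a last new blister on Day 1 is dated Week 2 (13 days late) or Week 4 (27 days late).
- For T spread evenly over Weeks 12 to 18, the first clear visit is Week 18: up to 6 weeks late, on average 18 − 15 = 3 weeks.

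**Delay against the planned interval.** The half-width is 2.201 × SD/√12 = 0.635 × SD. At SD 11 days it is 7.0 days; at SD 16 days, 10.2 days. A 7-day shift is about as large as the half-width, so coverage must fall well below 95%. A 21-day shift is 21/10.2 = 2.1 to 21/7.0 = 3.0 half-widths, so coverage is close to nil.

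**Simulation of the mean and its 95% t interval, n = 12.** The distributions are assumptions.
- Set A: 40,000 trials per scenario; lognormal (median 21 or 28 days), uniform on Days 1–56, and exponential (median 14 or 28 days), all truncated at Day 56; true mean 16–28 days, SD 11–16 days.
- Set B: 20,000 trials per scenario; gamma truncated at Week 10; true mean 3.0–5.3 weeks, SD 1.0–2.4 weeks.

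| Date used | Set A: bias (days) | Set A: coverage | Set B: bias (weeks) | Set B: coverage |
|---|---|---|---|---|
| Exact | 0 | 93–95% | 0.00 | 94–95% |
| First clear visit | +6.8 to +7.8 | 55–75% | +0.98 to +1.02 | 24–79% |
| Visit closing a clear interval | +20.8 to +21.8 | under 1% | +2.98 to +3.02 | 0–1.5% |
| Midpoint of the interval containing T | within 0.8 | 93–95% | within 0.02 | 94–96% |

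In Set B, first-clear-visit coverage rises with the SD: 24% at 1.0 week, 51–55% near 1.5, 64–67% near 1.8, and 72–79% at 2.2–2.4.

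**The median.** Reporting the named endpoint does not remove the shift. In Set A the visit-dated median was late by 6.5–7.6 days (first clear visit) and 20.5–21.6 days (closing visit).

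**An interval-censored analysis.** A Weibull interval-censored fit (600 trials per scenario, true medians 3.75, 4.66 and 4.70 weeks) had median bias of 0.01–0.08 weeks. The visit-dated medians in the same scenarios were late by 0.99–1.14 and 2.99–3.14 weeks. The data were generated from a Weibull, so this is a favourable test. The Turnbull estimator was not simulated.

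**The case against.** The plan never says that the visit date is the event date. An examination can include taking a history, and the inclusion criteria already use counts of new bullae over 3 days judged by the investigator or referring physician. Midpoint dating is equally compatible with the text and nearly unbiased. This stands: what the documents show is a missing rule and an analysis that ignores the gap between visits. The 1- and 3-week figures are conditional on how a site fills the gap. It does not remove the point, because no on-treatment date is provided for.

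A reader might infer that the 95% interval simply misses the true mean. The figures do not support that in general. With first-clear-visit dating it under-covers, but it still contains the mean in most trials once the SD is about 1.5 weeks or more. Near-certain missing belongs only to the closing-visit rule.

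A reader might also take all 3 weeks as measurement error. About 2 of them come from requiring a clear 2-week interval, which is close to Supplemental 1's consolidation phase. If that window is part of the intended event, only the remaining week is visit-grid delay.

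Finally, the study is exploratory, single-arm and without a test, and a 7-day shift is similar to the sampling half-width of 7–10 days. That limits the consequence. But sampling error is what the interval is meant to show; the shift is not shown at all.

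**Conclusion.** The point holds in this form: cessation is interval-censored, the plan analyses it as exact, and no dating rule is given. First-clear-visit dating makes mean and median about 1 week late. Coverage of the 95% interval for the mean then falls to about 55–75% at assumed SDs of 11–16 days, and 24–79% over SDs of 1.0–2.4 weeks. Closing-visit dating puts the event about 3 weeks after the last new blister (2 weeks window, 1 week grid), and the interval almost never covers the mean time of the last new blister. After Week 12 the grid widens to 6 weeks.

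The average delays follow from the visit schedule and barely depend on the distribution. The coverage figures rest on assumed distributions, a t interval, and lasting cessation by Day 56 or Week 10. No test or decision rule is affected. The harm is a shifted estimate with misleading precision in a study meant for estimation. The change is worth making because it is cheap.

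**What to change.** 1. In Primary Outcome Measures and the Primary Analysis paragraph, define the event date as the date of the last new blister. State any blister-free window separately, as confirmation, and date the event back to the last new blister.
2. Add one case report form question at each existing visit: date of the most recent new blister, checked against that visit's examination and photographs.
3. Where the date is unknown or unreliable, treat the time as interval-censored between the last visit with and the first visit without new blisters, including the Week 12–18 gap. The bounds must match how visits are scored. If a visit is scored on blisters new since the previous visit, the last new blister lies between the last visit with new blisters and the visit before it.
4. Estimate the median by an interval-censored method (Turnbull or parametric) with a 95% confidence interval, in place of the mean, SD and interval of visit dates. A bootstrap is one option. Another is order-statistic limits widened to the interval bounds: the 3rd smallest lower bound to the 10th smallest upper bound. With 12 patients the exact-time version has coverage 1 − 2 × (1 + 12 + 66)/4096 = 96.1%, and widening cannot reduce it.

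Cost: one form question and some analysis-plan wording, with no added visits or procedures. Recalled dates are subjective in an elderly, open-label population, so report the purely visit-based interval-censored result as a sensitivity analysis. The confidence interval for the median will be wider than the one now planned for the mean.
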